6 STUDY SETTING

The study will be performed on all paediatric inpatient wards at Royal Manchester Hospital. The research team will be based on the CCRF (Children's Clinical Research Facility) and will move to each ward as required to provide VRH for procedures. Participants will be accessed via identification by clinicians performing painful procedures.

Royal Manchester Children's Hospital is the busiest children's hospital in the UK. Venepuncture and cannulation are routinely performed by a wide variety of staff including doctors, nurses and the IV access team. It is therefore an ideal location to conduct this study. Participants will undergo recruitment, discussion with the research team, consent and procedure all in the same location within

Virtual Reality for Pain and Anxiety in Children

Royal Manchester Children's Hospital. Participation in the study will not impact upon patient care and will not require patients or parents to move anywhere or do anything they would not already be doing as part of their inpatient stay.

7 SAMPLE AND RECRUITMENT

7.1 Eligibility Criteria

7.1.1 Inclusion criteria

Any child of age 5-12 years who are an inpatient in Royal Manchester Children's Hospital over a 4 week study period will be considered for consent if they require venepuncture or cannulation for a medical reason as determined by their lead medical team.

All individuals will be considered for inclusion in this study regardless of age, disability, gender reassignment, marriage and civil partnership, pregnancy and maternity, race, religion and belief, sex, and sexual orientation except where the study inclusion and exclusion criteria EXPLICITLY state otherwise.

7.1.2 Exclusion criteria

Children under the age of 5 years (may not fit the headset, may become upset) and over the age of 12 years (pubertal, more mature understanding and expectations) will be excluded.

Children not needed venepuncture or cannulation will not be invited.

Children who have worn VRH previously and recognise dizziness/sickness or other ill health symptoms will not be asked to consent.

Parent/ guardians of children who are unsure about VRH will be excluded.

Parents will not be excluded if their first language is not English. As far as possible a translator will be arranged to translate child/parent responses and give feedback.

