2 RATIONALE

We want to know if it is feasible to use VRH for distraction during painful procedures in paediatric inpatients. Utility of this cannot be extrapolated from outpatient/clinic/emergency department studies.

Virtual Reality for Pain and Anxiety in Children

We want to know if this is acceptable to patients, parents and clinicians and if they would be keen for this to become routine practice for painful procedures in our hospital.

Painful procedures are a source of significant stress and anxiety to children who are inpatients in hospital and it is our duty as clinicians to understand if there is a way in which we can reduce this stress and anxiety.

If use of VRHs during painful procedures was found to be simple, effective and desirable this could be easily and quickly rolled out to all of our inpatient wards and later to other hospitals. This could have a significant impact upon the inpatient stay of children all over the country.

This project will be conducted in accordance with the study protocol and the ethical principles outlined by Good Clinical Practice (GCP) and the Declaration of Helsinki in its most current version.

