4.2 Outcome

1. Perceived and reported pain/anxiety scores for children undergoing venepuncture or cannulation with VRH.
2. Change in heart rate before, during and after painful procedure
3. Clinicians' feedback on the use of VRH in inpatient painful procedures

5 STUDY DESIGN and METHODS of DATA COLLECTION AND DATA ANALYSIS

Practitioners will be encouraged to contact the research team each time they are to perform a procedure between 0830H and 1600H and, unless already with another child using VRH, the research team will come to speak to parents to consent to the study. If consent is obtained then the procedure will be performed using current standard care as well as use of a VRH. The Oculus Go is a cheap and quick to set up headset. Off the shelf software will be selected that will distract but not require the movement of both arms. Software such as The Blu, Ocean Rift and Pet lab will be selected, dependent upon the age of the patient.

VRH will be brought to the room planned for procedure and set up for the child as part of the preparation for venepuncture/cannulation. Prior to application of VRH children will be asked to score their current pain score using the Wong Baker Faces Score (WBFS)¹. This will be transcribed by the researcher. VRH use will be commenced at least 3 minutes prior to commencement of painful procedure. The procedure will then be performed by the practitioner and VRH supervised by parent(s). The researcher will not participate in the procedure beyond initial setup of the VRH to ensure real world feasibility is being tested for. Once the procedure is completed, the child will be allowed to continue using the VRH while clinicians and parents involved in the procedure fill in the feedback forms.

Feedback forms for parents will focus on perceived pain score and short qualitative review regarding acceptability, whether they would consider repeat application at subsequent venepuncture procedures, if VRH was well tolerated and whether they felt it helped. Feedback from clinicians will focus on ease of use of VRH, if they felt it facilitated procedure or whether it was felt to prolong the procedure. Forms will be filled in by parents and clinicians themselves and then handed to the researcher.

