Children will then have the VRH removed and be asked to score their current pain again using the WBFS. Children's WBFS will be compared pre and post procedure. Assessment of acceptability/feasibility for children will be based on 3 **questions** – 1. Do they like it, 2. Was VRH wear comfortable and 3. Did they feel unwell whilst wearing VRH. Questionnaire answers will also be used to design future trials and bespoke VR software.

Questionnaires will then be pseudonymised and transcribed on to a secure computer for analysis of data. Interpretation of data will be performed by the clinical research team. Any statistical analysis required will be performed using SPSS Statistics 25 on pseudonymised datasets. Paper questionnaires will be kept in a locked drawer, in a locked room, on a locked research unit where access is only via swipe card. Access to paper questionnaires and digital data will only be for the immediate clinical research team of [name] and [name].

¹ Wong-Baker FACES Foundation (2018). Wong-Baker FACES® Pain Rating Scale. Retrieved [11/10/19] with permission from <http://www.WongBakerFACES.org>

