7.2 Sampling

7.2.1 Size of sample

For this feasibility study, we aim to recruit 32 children during a 4 week period. Using the primary outcome acceptability of patient use, 32 children will enable us to identify our acceptability target of 75% of patients with 95% CI 56.6-88.5% (Clopper-Pearson exact). This number will also provide meaningful representation of a spread of gender, age groups, complexity of underlying illness, cultural and ethnic backgrounds to design future studies.

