7.3.1 Sample identification

Clinicians who regularly undertake venipuncture and cannulation in the hospital will be made aware of the study two weeks ahead of the beginning of data collection via posters and emails. Clinicians will be responsible for informing the research team of eligible patients for the study. All patients who meet the eligibility criteria and are highlighted to the research team will be included.

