8 ETHICAL AND REGULATORY CONSIDERATIONS

8.1 Assessment and management of risk

Some children may not prefer to keep the Virtual Reality Headsets over their faces. They may also feel dizzy and be sick. If so, the headsets will be immediately removed and not re-applied. The child will continue to have the routine procedure without application of VRH.

If parents or children are uncomfortable with the application of technology, they will not be consented and VRH will not be applied.

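### Acceptability is measured only in families already willing to try the headset, and nothing counts how many were offered it or refused it

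*Protocol*

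**What the plan says.** **Who can enter.** Section 7.1.2 of the protocol says "Parent/ guardians of children who are unsure about VRH will be excluded". Section 8.1 adds "If parents or children are uncomfortable with the application of technology, they will not be consented and VRH will not be applied". Section 7.2.2 then admits eligible children for whom consent is given.

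**What is measured.** Section 7.2.1 names the primary outcome and target: "Using the primary outcome acceptability of patient use, 32 children will enable us to identify our acceptability target of 75% of patients", with an exact 95% interval of 56.6-88.5%. Section 5 describes how it is obtained, after the headset has come off: "Assessment of acceptability/feasibility for children will be based on 3" questions, on liking, comfort and feeling unwell. Parents are asked, among other things, "whether they would consider repeat application at subsequent venepuncture procedures".

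**What the study wants to learn.** Section 2 says "We want to know if this is acceptable to patients, parents and clinicians and if they would be keen for this to become routine practice", and looks ahead to use on all inpatient wards and later in other hospitals. Section 4.1 plans a large RCT in the same setting.

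**How families reach the team.** Section 7.3.1: "Clinicians will be responsible for informing the research team of eligible patients for the study". Under section 5 the team attends when contacted, between 0830 and 1600, and "unless already with another child using VRH, the research team will come to speak to parents to consent to the study".

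**What is not there.** The outcomes in 4.2, the data collection in 5, and sections 7.2 to 7.3.2 contain no count of families offered VRH, accepting it, or declining it, and no record of reasons.

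**The concern.** Entry to the sample depends on a favourable attitude to VRH, and attitude to VRH is what the primary outcome measures. Families most likely to find it unacceptable leave before anyone asks them. The parents' repeat-use item, the one closest to the Rationale's routine-practice question, is answered by the same willing families.

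Two things are at stake. First, a reader may take the acceptability figure as an answer for inpatients and their parents in general, when it describes those who had already agreed to try the headset. Second, uptake is a feasibility result in its own right and bears on recruitment to the planned RCT. This goes beyond what can be left to an analysis plan: a plan can define a proportion, but it cannot supply refusals that were never recorded.

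**Working it through.** **1. Reproduce the stated figure.** Inputs from section 7.2.1: n = 32, target 75%, so 0.75 × 32 = 24 children. The two-sided 95% Clopper-Pearson limits are the 0.025 quantile of Beta(x, n − x + 1) and the 0.975 quantile of Beta(x + 1, n − x). For 24/32 these are 56.6% and 88.5%, as the protocol states. The arithmetic is right; the question is whom the interval describes.

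**2. Acceptability among all families offered VRH.** The protocol gives no refusal rate, so two quantities are assumed:

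- d = share of families offered VRH who decline because of it;
- q = share of those decliners who would have found it acceptable, from 0 (none) to 0.75 (same as users).

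Acceptability among all offered = 0.75 × (1 − d) + q × d.

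| d (assumed) | q = 0 | q = 0.75 |
|---|---|---|
| 4% | 0.75 × 0.96 = 72.0% | 75% |
| 10% | 0.75 × 0.90 = 67.5% | 75% |
| 20% | 0.75 × 0.80 = 60.0% | 75% |
| 30% | 0.75 × 0.70 = 52.5% | 75% |

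The only related figure in the protocol is the 96% enthusiasm among more than 300 people surveyed (section 1). Read as d = 4%, it implies a loss of 0 to 3 points, well inside the stated interval. It is a weak proxy: the group was different, and lack of enthusiasm in a survey is not refusal before a needle procedure on a ward.

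**3. What a tally would give.** Uptake = accepted / offered, with 32 accepted and assumed numbers offered:

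| Offered | Uptake | Exact 95% CI |
|---|---|---|
| 34 | 94.1% | 80.3-99.3% |
| 36 | 88.9% | 73.9-96.9% |
| 40 | 80.0% | 64.4-90.9% |

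**4. Worked case (hypothetical).** Of 40 families offered VRH, 32 accept, 4 decline because of VRH, 1 gives no reason and 3 decline for other reasons (32 + 4 + 1 + 3 = 40).

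- Uptake: 32/40 = 80.0% (64.4-90.9%).
- VRH-related refusals: 4/40 = 10.0% (2.8-23.7%).
- Optional sensitivity figure, counting VRH-related and no-reason refusals as not acceptable and leaving out other-reason refusals: 24/(32 + 4 + 1) = 24/37 = 64.9% (47.5-79.8%).

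**The case against.** Any consented study of a headset observes only people who agree to wear it, so most of this selection cannot be avoided. The outcome is worded as acceptability of use, objective 1 in section 4.1 concerns use, and the wider question appears in the Rationale and not among the objectives. Reluctance that emerges after consent can still lower the result: section 8.1 expects some children not to keep the headset on or to feel unwell, and section 5 asks about both comfort and feeling unwell. The size of any overstatement is unsupported by data, and every range above ends at 75%, meaning no bias. The team may also keep a screening log in site paperwork.

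Much of this stands. Selection by consent is unavoidable, the primary proportion is valid for willing users, and the magnitude is unknown. A tally would also be imperfect: refusing a study is not the same as refusing VRH in routine care, reasons may be missing, and unsure families may be filtered out by clinicians before the team hears of them.

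None of it removes the gap. Because selection is unavoidable, its extent is worth counting. The Rationale's question is one the protocol says the study is meant to answer. No section provides for a log, and section 7.3.1 speaks only of including those brought to the team's attention.

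**Conclusion.** The concern holds, as a point to consider. Sections 7.1.2 and 8.1 restrict the sample to families comfortable with VRH, and no part of the protocol counts offers, uptake or VRH-related refusals. The 75% target and its interval apply to willing users. As an answer to the Rationale's question they are likely to be too high, on the assumption that families who decline because of VRH would accept it less often than users. The amount is unknown: 0 to 3 points if the section 1 survey is any guide, and up to 15 points at an assumed 20% VRH-related refusal (75 − 60). No stated figure or primary analysis needs to change. The firm loss is the uptake rate, which the study as written would not produce.

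**What to change.** Leave the consent, exclusion and headset-removal rules as they are.

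1. **Keep an anonymous tally.** The research team counts children notified, offered VRH, accepted, declined or excluded for VRH reluctance, declined for other reasons, and declined without a reason. Where the referring clinician reports it, also count children not referred because the family was unsure. Count separately those not approached because of past VRH symptoms. State that the tally covers only families who reached the team.
2. **Report uptake** (accepted / offered, exact CI) and the number of VRH-related refusals beside the primary proportion.
3. **Add one sentence to 7.2.1** saying that the 75% target applies to children of families willing to try VRH.
4. **Optional:** one sensitivity proportion built as in the worked case. Describe it as a conservative figure for families reached by the team, not as a bound for all inpatients, and do not judge it against 75%.

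If the full set of categories is too much for a 4-week study, a count of offered, accepted and declined would still give uptake, though not the reasons.

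The cost is a one-page form without personal data, one sentence, and one or two extra proportions. The downsides are that the tally misses families never referred, and that a less favourable figure may stand beside the headline result.

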7.2 Sampling

7.2.1 Size of sample

For this feasibility study, we aim to recruit 32 children during a 4 week period. Using the primary outcome acceptability of patient use, 32 children will enable us to identify our acceptability target of 75% of patients with 95% CI 56.6-88.5% (Clopper-Pearson exact). This number will also provide meaningful representation of a spread of gender, age groups, complexity of underlying illness, cultural and ethnic backgrounds to design future studies.

7.2.2 Sampling technique

All children who are identified as eligible by clinicians will be considered for the study. If they meet the inclusion criteria and consent to the study they will be included. As this is purely a feasibility study no sampling technique beyond this will be required.

7.3 Recruitment

Virtual Reality for Pain and Anxiety in Children

The study will be advertised a month and two weeks prior to the start via email targeting all doctors, IV practitioners and nurses within Royal Manchester Children's Hospital informing them of the availability of VRH headsets for distraction during venepuncture/cannulation. Posters detailing similar information will be distributed across all paediatric wards and in treatment rooms. Information will also be available on the trust intranet.

7.3.1 Sample identification

Clinicians who regularly undertake venipuncture and cannulation in the hospital will be made aware of the study two weeks ahead of the beginning of data collection via posters and emails. Clinicians will be responsible for informing the research team of eligible patients for the study. All patients who meet the eligibility criteria and are highlighted to the research team will be included.

7.3.2 Consent

Informed consent will be taken from parents of patients recruited to the study. Both patients and parents will be given a written information sheet to read prior to consent. Once they have read this they will have the opportunity to ask any questions of the research team. If they agree to take part then parents will be asked to sign a consent form. Children will be given the option to sign an assent form if they wish but this will not be compulsory.

8 ETHICAL AND REGULATORY CONSIDERATIONS

8.1 Assessment and management of risk

Some children may not prefer to keep the Virtual Reality Headsets over their faces. They may also feel dizzy and be sick. If so, the headsets will be immediately removed and not re-applied. The child will continue to have the routine procedure without application of VRH.

If parents or children are uncomfortable with the application of technology, they will not be consented and VRH will not be applied.

8.2 Research Ethics Committee (REC) and other Regulatory review & reports

- Before the start of the study, a favourable opinion will be sought from the Research Ethics Committee (REC) and Health Research Authority (HRA)

Regulatory Review & Compliance

- Before we enrol patients into the study, the Chief Investigator will ensure that appropriate approvals from participating organisations are in place.
- For any amendment to the study, the Chief Investigator or designee, in agreement with the sponsor will submit information to the appropriate body in order for them to issue approval for the amendment. The Chief Investigator or designee will work with the R&D department) so they can put the necessary arrangements in place to implement the amendment to confirm their support for the study as amended.
- The study will be subject to the annual Self-Assessment questionnaire, for completion by a member of the research team

Amendments

Virtual Reality for Pain and Anxiety in Children

If amendments to the protocol are required, this will be determined by the Chief Investigator who will be ultimately responsible for this. This will be discussed with the Sponsor before submission to the ethics committee

8.3 Peer review

The study protocol has been reviewed by the funder who are Manchester University NHS Foundation Trust. The process for funding approval involved an independent peer review by at least two experts. This review was part of the application for funding under the DiTA funding offered by Manchester University NHS Foundation Trust.

8.5 Protocol compliance

One of the strengths of our protocol is its simplicity and this will significantly improve compliance. Accidental protocol deviations can happen at any time and in this circumstance it would be reported immediately to the Chief Investigator and Sponsor. Any recurrent deviations from the protocol will not be considered acceptable and will be actioned immediately.

8.6 Data protection and patient confidentiality

Only the direct clinical care team will have access to the patients' personal data. The research team (comprising of doctors in the Children's hospital) will not review medical/surgical data for the patient as this is irrelevant to the study and will contravene Data Protection and Confidentiality regulations as per standard clinical practice.

The study data will be analysed by our research fellow at the Royal Manchester Children's Hospital. The results will be discussed with the senior statistician who is also based in the same NHS Trust.

Data will be stored in the department of Paediatric Endocrinology at the Royal Manchester Children's hospital, on a departmental server kept secured by username and passwords. Access to the department is swipe card controlled and the room where the NHS computers with departmental drives are based is secured by a combination lock. Storage of research data will be overseen by the research team. Paper data will be stored in fire proof filing cabinets and kept under lock and key.

Storage and destruction of research data will be carried out in line with trust archiving policies

This is a feasibility and pilot study upon which a formal clinical trial will be launched. While this is an intervention related study, the primary aim is feasibility and applicability rather than efficacy.

The data custodian is the Chief Investigator.

8.7 Indemnity

NHS indemnity applies as this is a trust sponsored study.

Equipment will be purchased using funding money and will be stored securely. There is no insurance in place for damage or loss to the equipment but this is considered to be very unlikely. If equipment was lost or damaged then replacement equipment could be borrowed from VREvo so as to allow completion of the study.

8.8 Access to the final study dataset

Virtual Reality for Pain and Anxiety in Children

Research will not be registered on a public database and data will be kept locally. Identifiable personal data will only be used at the time of the venepuncture/cannulation procedure and will not be used at any other time. We will pseudonymise data for analysis and anonymise data when sharing with the statistician, thereby breaking the link between patient identity and relevant data. Publication of data will only include high level outcomes with no patient identifiable information. The only people with access to the original data will be [name] and [name]. Pseudoanonymised data will be shared with the statistician.

Parents and children will be asked to contact the research team by e-mail to arrange separate occasions to discuss results. As the study does not collect patient identifiable information the research team will be unable to contact the family after acquisition of data.

The study team will prepare a manuscript with the final study results and this will be submitted to a peer review journal for publication and subsequent dissemination of results.

